4.3 Randomization and Blinding

This is an observer-blinded clinical study. Both the study subjects and the study personnel involved in safety assessment (observers) will be blinded to treatment assignments. Designated unblinded study-site personnel will be responsible for preparing and administering the study injection.

In Part 1, subjects will be randomized 1:1:1 to Group 1, 2, or 3. In Part 2, subjects will be randomized 1:1 to 1 of 2 groups (ie, either Group 1 and 3 or Group 2 and 3) as determined from Part 1. Randomization will be stratified by site.

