- Grade 4 post-injection reaction (PIR) within 7 days after any study injection
- Clinically significant Grade 3 or higher systemic reaction (eg, angioedema, generalized urticaria) within 7 days after any study injection
- Grade 3 or 4 hypotension within 24 hours of any study injection
- Grade 3 or 4 respiratory reaction or symptoms occurring within 24 hours of any study injection
- Any life-threatening AE, regardless of relationship to study drug
- Any AMI
- Any confirmed immune-mediated AE
- Violation of protocol eligibility criteria
- Subject received prohibited medications
- SAE assessed as a suspected adverse reaction (SAR) or adverse reaction (AR)
- Subject becomes pregnant or begins breastfeeding

If the subject is not eligible for subsequent study injections, **the subject will not be withdrawn from the study**, but, if possible, will be followed for safety through End-of-Study (EOS) Visit.

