7.5 Concomitant Medications

7.5.1 Prohibited Treatments or Therapies

The following non-study medications are prohibited:

- **Any licensed COVID-19 vaccine or inactivated vaccine (including vaccines containing mRNA or CpG)**
 - :S 14 days prior to each study injection through 14 days after each study injection
- **Any live vaccine**
 - :S 28 days prior to each study injection through 28 days after each study injection

- **Other concomitant medications**

- :S 28 days prior to vaccine injection (Day 1) through 28 days after the third study vaccine injection Week 26 (Day 183):
 - Systemic corticosteroids (more than 3 consecutive days) or other immunomodulators or immunomodulators immune suppressive medication, with the exception of inhaled steroids
 - Any other investigational medicinal agent
- :S 90 days prior to vaccine injection (Day 1) and through 28 days after the third study vaccine injection Week 26 (Day 183):
 - Granulocyte or granulocyte-macrophage colony-stimulating factor
 - Immunoglobulins or any blood products
 - Antisense oligonucleotides
 - Drugs/investigational agents with very long half-lives (defined as 2' 60 days)
- At any time prior to vaccine injection (Day 1) and through 28 days after the third study vaccine injection Week 26 (Day 183):
 - DNA plasmids or other genetic therapy intended to integrate permanently into host cells

If a subject requires treatment that is prohibited, **the subject will not be withdrawn from the study** but will be followed for safety through Week 56.

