9.7 Early Discontinuation/End of Study

An EOS Assessment is required at Week 56 (Day 393) in alignment with the protocol, GCP as defined in International Council for Harmonisation (ICH) guidelines and US Code of Federal Regulations (CFR), and applicable local regulatory requirements. The EOS procedures will be performed as an Early Discontinuation assessment at least 28 days after the last study injection if the subject is permanently discontinued early from the trial. Investigators are responsible for monitoring the safety of subjects throughout the course of the study and for providing appropriate medical care. The investigator will perform all tasks directly or is responsible for overseeing and training qualified site personnel as delegated to perform study tasks. In addition, investigators are responsible for alerting Dynavax to any event that seems unusual and for reporting all AEs, SAEs, pregnancies, and deaths in the appropriate CRFs.

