11 STATISTICAL METHODS

Part 1 objectives will be evaluated descriptively. The administration method of vaccine utilized in Part 2 of the study will be selected by Dynavax in consultation with the DoD after Day 57 immunogenicity data become available to determine whether the GMC 1 month after 2 doses of rF1V vaccine with CpG 1018 using the selected administration method is at least 2 times higher than that 4 weeks after 2 doses of rF1V vaccine in Group 3.

The proposed statistical planning for Part 2 is presented according to the objectives. No multiplicity adjustments are made, and all statistical tests will be conducted at 5% two-sided Type I level unless otherwise specified.

All analyses of demographics, medical history, and safety will be summarized in a descriptive manner. In general, continuous variables will be summarized by number of subjects, mean, standard deviation, median, quartiles, minimum and maximum, and categorical variables will be summarized by number and percentage of subjects in each study group as appropriate. No specific safety hypotheses will be tested.

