11.1 Sample Size Considerations

Part 2 primary objective 1 is to assess the utility of a 2-dose schedule of rF1V vaccine with CpG 1018 as measured by reduction in time to onset of predicted rF1V protection. The predicted protection will be based on a [REDACTED] titer threshold. Previous animal studies have established protective efficacy in animals. Since a human efficacy study is not feasible, an immunobridge from animal data to human data via the [REDACTED] test will be used to predict the protective efficacy in humans using a regression model. An initial predicted protection threshold will be calculated based on the data generated in this study in Group 3 after 3 doses of rF1V vaccine. Once the threshold is identified, it will be applied to the study groups in Part 2 of the study to evaluate the objectives. In addition to the previous animal studies conducted to establish protective efficacy, a new animal model utilizing rF1V vaccine with CpG 1018 will be developed to establish the protective level of antibody for CpG 1018 containing vaccines. Additional analyses will include a predicted protection threshold that will be calculated based on the data generated under the new animal model after 2 doses of rF1V vaccine with CpG 1018. In both instances, the animal-to-human immunobridge and the identification of the predicted protection thresholds will be documented in a separate report.

A similar approach was used to analyze the previous Phase 2a and Phase 2b study data using the animal model from the previous animal studies. Thresholds that corresponded to 50% predicted protective efficacy in humans were established for those trials. In a pooled analysis of these previous immunobridge studies, 93% (95% Clopper Pearson confidence interval [CI] = 85%, 98%) of subjects reached the predicted protection threshold.

It is assumed that a similar percentage of the subjects in Group 3 will reach the threshold identified in this study. When this threshold is applied to both Part 2 study groups, a similar

lower bound of the 95% CI is desired across the groups. Table 11-1 shows the lower bound of 95% Clopper Pearson CI for different observed levels of predicted protection assuming 85 of the 90 planned subjects (Part 1 N = 20 and Part 2 N =70) will have data available for the evaluation. Thus, with a predicted protection level of 93%, the lower bound of the 95% CI would be 85%.

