APPENDIX 1: SCHEDULE OF TRIAL EVENTS (CONT'D) FOOTNOTES

Screening ^a	Routine laboratory tests (serum chemistry, hematology) for screening should be performed within 28 days prior to enrollment. Subjects may have the screening window extended an additional 7-calendar days if they have equivocal laboratory results or if they cannot be enrolled during the screening window. The screening window may only be extended one time and must have prior approval by the sponsor's medical monitor.
EOS/Safety F/U ^b	A mandatory EOS/Safety Follow-up telephone call will be performed [32 days] [3] after the administration of the last study vaccine. If a subject receives less than 3 doses of vaccine, their EOS visit will be 28 days after their last dose. The EOS visit procedures will be performed as an Early Discontinuation visit if the subject is permanently discontinued early from the trial.
Telephone Call ^c	Telephone call Day 4 (Part 1 only) and EOS
Part 1 Final immunogenicity Assessment ^d	Part 1 final immunogenicity assessment will be conducted based on Day 57.
Demographics/Medical History/Prior Medications ^e	Demographic and baseline characteristics of sex, race, ethnicity, age, weight, and height, and medical history will be collected. Report complete medication history for 28 days prior to Baseline (Day 1).
Vital Signs ^f	Includes oral temperature (only at trial injection visits), heart rate, respiratory rate, systolic and diastolic blood pressure.
Physical Examination ^g	The investigator or qualified designee will conduct physical examinations. A complete physical examination is conducted at Screening. A symptom-directed physical exam is conducted at all other designated time points.
HIV, HBV, HCV Testing ^h	HIV, HBV, HCV testing.
Pregnancy Test ⁱ	For females of childbearing potential, a serum pregnancy test will be collected at screening and must be negative for the subject to participate. A urine pregnancy test must be negative within 24 hours prior to administration of each study vaccine. The test must be negative for the subject to receive study injection.

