5.3 Immunogenicity Population

The modified intent-to-treat (mITT) population will comprise all eligible subjects who received at least 1 dose of study vaccine and have a post-injection immunogenicity evaluation.

The per-protocol (PP) population for the immunogenicity analyses will comprise Groups 1 and 2 subjects who received 2 doses of study vaccine and Group 3 subjects who received 3 doses of study vaccine, have no major protocol deviations (see Section 8.2), and have immunogenicity data obtained within the study visit window at Day █ for Groups 1 and 2 and Day █ for Group 3.

Note: the PP population definition and major protocol deviations in Section 8.2 are updated from the Protocol Amendment 5.

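### After injections stop, the protocol does not secure the Week 8 antibody sample and its end-of-study rules conflict, so the Week 8 GMC ratio can become a completers' ratio

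*Protocol*

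**What the plan says.** **Stopping injections.** Protocol 5.3 lists the triggers for withholding further injections and says that the subject is not withdrawn but "if possible, will be followed for safety through End-of-Study (EOS) Visit". Section 7.5.1 says the same of a subject who needs a prohibited treatment: not withdrawn, "but will be followed for safety through Week 56". Safety is the only purpose named in either place.

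**Leaving the study.** This is a separate event, covered by 5.4 and 9.7. Section 9.7 requires EOS at Week 56 (Day 393) and adds, for subjects permanently discontinued from the trial: "The EOS procedures will be performed as an Early Discontinuation assessment at least 28 days after the last study injection".

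**Appendix 1.** Footnote b sets the EOS visit at 28 days after the last dose for anyone who has had fewer than three doses. Footnote c gives the mode of contact: "Telephone call Day 4 (Part 1 only) and EOS". The EOS/Early Discontinuation column is headed as a telephone call.

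**Analysis.** SAP 5.3 defines mITT, the primary immunogenicity set, as "all eligible subjects who received at least 1 dose of study vaccine and have a post-injection immunogenicity evaluation". The PP set, which is the sensitivity set, requires two doses in Groups 1 and 2 and three in Group 3. SAP 6.3 imputes nothing except dates. The estimand paragraphs in SAP 8.6 give no rule for stopped injections. Part 2 primary objective 2 is judged on the point estimate of the Week 8 GMC ratio reaching 2.

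**The concern.** The mITT definition is built to keep a subject who had one dose and then stopped. The conduct rules do not ensure that this subject has a Week 8 titre. If the titre is not drawn, the subject drops out of the Week 8 GMC and no later analysis can recover the value. The PP analysis gives no check, because it leaves out the same subjects.

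Some of the 5.3 triggers are reactions to injection, which an added adjuvant could make more frequent in one arm. One-dose subjects would be expected to have lower titres at Week 8 than two-dose subjects. Losing more of them from the CpG arm would raise that arm's GMC. The criterion is a bare point estimate, so no confidence bound absorbs such a shift.

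**Working it through.** **1. Follow one subject through the rules.** Protocol 9.4.1 places the injection visits at Days 1, 29 and 183. Week 8 is Day 57.

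- Stopped after dose 1, footnote b: EOS by telephone at 1 + 28 = Day 29, before the Day 57 sample.
- Stopped after dose 2, footnote b: EOS by telephone at 29 + 28 = Day 57, the day of the Week 8 sample.
- Either subject under 7.5.1: follow-up to Week 56.
- Either subject under 9.7, if still in the study: EOS at Day 393.

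These rules cannot all apply to the same subject. None of them says whether the Day 57 sample is drawn once injections have stopped.

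**2. The plan's own figure.** The only sample-size figures are the Clopper-Pearson limits in Protocol Table 11-1 at N = 85. They reproduce:

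- 81/85: 88.4% to 98.7% (stated 88%, 99%)
- 79/85: 85.3% to 97.4% (stated 85%, 97%)
- 77/85: 82.3% to 95.8% (stated 82%, 96%)

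No SD, power or sample size is given for the GMC ratio. Section 11 says "all statistical tests will be conducted at 5% two-sided Type I level", but the 2-fold criterion is not a test.

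**3. Inputs for the bias.** Allocation is equal ("In Part 2, subjects will be randomized 1:1 to 1 of 2 groups"; 1:1:1 in Part 1), giving 90 planned per arm. Section 11.1 assumes that "85 of the 90 planned subjects (Part 1 N = 20 and Part 2 N =70) will have data available for the evaluation", so 5/90 = 5.6% have no data, for any reason. Assumed, because the documents give neither: the number k of one-dose losses per arm, and the factor r by which a one-dose titre falls below a two-dose titre at Week 8.

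**4. Formula.** If a share f = k/90 of an arm is missing and its GMC would have been r-fold lower, then all-treated GMC = observed GMC × r^(−f). The observed ratio is therefore inflated by r^(f_CpG − f_Group 3).

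| Losses, CpG arm only | r = 3 | r = 10 | All-treated ratio that shows as 2.00 |
|---|---|---|---|
| 1 of 90 | 1.01 | 1.03 | 1.98 to 1.95 |
| 2 of 90 | 1.02 | 1.05 | 1.95 to 1.90 |
| 5 of 90 | 1.06 | 1.14 | 1.88 to 1.76 |

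- Equal losses with equal r: 1.00.
- Five CpG losses against three control losses, r = 10: 10^(2/90) = 1.05.
- Wider range, r = 2 to 50, five losses in the CpG arm only: 1.04 to 1.24. Even 1.24 × 1.5 = 1.86, so a ratio of 1.5 does not reach 2 within the planned loss.

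**5. Against sampling error.** With an assumed log10 SD of 0.3 to 0.6 and 85 per arm, SE = SD × √(2/85), which is 1.11- to 1.24-fold. One or two losses at r = 10 shift the ratio by less than one SE. For an all-treated ratio of 1.9, the chance of meeting the criterion rises from 31–40% to 50% with two such losses.

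**6. Opposite direction.** If subjects lost after dose 2 would have responded 1.5- to 3-fold higher than the rest of the CpG arm, the ratio falls: 1.5^(−1/90) = 0.996 for one loss, 3^(−5/90) = 0.941 for five.

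**7. Part 1.** With 20 per group, one one-dose loss in a CpG group inflates its ratio to Group 3 by 3^(1/20) = 1.06 to 10^(1/20) = 1.12. The Day 57 ratio informs the choice of administration method.

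**The case against.** A reader might infer that the Week 8 ratio will be computed without the subjects stopped for reactions. The documents do not say that. No sentence cancels the Day 57 draw; 5.3 keeps the subject in the study, visits follow Appendix 1, and mITT does not exclude stopped subjects. Describing follow-up as being for safety states a purpose and does not bar blood samples. This stands, and it limits the finding to unspecified sampling and conflicting rules.

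Other points also stand:

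- Stopping injections and leaving the study are different events. Early leavers who have had dose 2 are not one-dose low responders.
- The 14% figure is a stacked worst case. The 85 of 90 is a general allowance for missing data, made for the predicted-protection table.
- Several triggers in 5.3 are not reactions: eligibility violations, prohibited medication, pregnancy.
- The protocol's own background does not suggest a large imbalance. In the hepatitis B programme any post-injection reaction occurred in 55.1% with CpG 1018 against 57.1% with the alum comparator.
- Section 8.2 pauses all dosing after certain events, which makes five unreviewed reaction stops unlikely.
- The extracted Appendix 1 table is broken, so the empty EOS cell for the rF1V sample is read from cell order. The telephone mode does not depend on that reading; footnote c states it.

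It can also be argued that a subject without dose 2 has no value 28 days after the second dose, so nothing is inflated. That depends on an estimand strategy that the SAP does not state, while its primary population admits one-dose subjects. Drawing the sample keeps either choice open.

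**Conclusion.** The point holds as a gap and a conflict in conduct rules. Sampling after stopped injections is unspecified. Footnote b conflicts with 7.5.1, and with 9.7 for subjects who remain in the study. A site that follows footnote b for a subject stopped after dose 1 loses the Week 8 titre, and neither mITT nor PP repairs this.

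The likely size is small: about 3% to 5% for one or two one-dose losses confined to the CpG arm at an assumed 10-fold lower titre, and about 6% to 14% if all five planned losses fall there (3- to 10-fold). It matters only for a ratio already near 2. Equal losses give little bias, and losses after dose 2 could move the ratio either way. The documents give no stopping rate and no one-dose titre, so they do not support a claim that the criterion would be met falsely. The change is still worth making, because it is cheap and undrawn samples cannot be recovered.

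**What to change.** - In 5.3 and 7.5.1, state that subjects who stop injections but stay in the study are followed for safety and immunogenicity, with all scheduled rF1V samples, including Week 8 and Week 30, still drawn.
- Reconcile footnote b, 5.3, 7.5.1 and 9.7, so that EOS timing does not end sampling before Week 8 or Week 30.
- For subjects who leave before those samples and agree, offer a blood draw at the early-discontinuation assessment, and mark it in Appendix 1.
- In SAP 8.6, state how stopped injections are handled, analyse these titres as observed in mITT, and add a sensitivity analysis of the GMC ratio for missing Week 8 values. The r^f calculation above, over a range of r, would serve.

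The cost is a few sentences and a mark in the schedule. For subjects who remain, the draws are already in the schedule. A few early leavers would have a clinic visit instead of a call, and the ratio may come out slightly less favourable.

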5.4 Removal of Subjects From the Study

Subjects may choose to withdraw from the study at any time. The reason for withdrawal will be recorded on the case report form (CRF).

Subjects may also be discontinued from the study by the investigator for any of the following reasons:

- Subject does not receive a dose of study vaccine

- Noncompliance with study procedures as determined by the investigator or sponsor
- At the discretion of the investigator if it is felt to no longer be in the best interest of the subject to remain in the study
- The sponsor decides to terminate the study

The investigator or designee should discuss with the medical monitor prior to withdrawing a subject from the study before study completion.

- If a subject discontinues, the End of Study (EOS) assessments should be completed. Required procedures are listed in [Section 9.7](#) and in the Schedule of Events ([Appendix 1](#)).
- Additional information about terminating the study may be found in [Section 6](#).

5.5 Replacement of Subjects

Subjects randomized and not treated may be replaced at the discretion of the Dynavax medical monitor.

5.6 Study Termination

The sponsor reserves the right to terminate the study at any time. Reasons for discontinuation of the study include but are not limited to:

- Inability to enroll sufficient subjects into the study
 - Good clinical practice (GCP) compliance issues that compromise the validity of the study
 - Emerging safety or efficacy data that deem the study unethical or impractical for continuation

Procedures for withdrawal of individual subjects can be found in [Section 5.3](#).

6 STUDY TREATMENT AND SUPPLIES

6.1 Study Treatments

6.1.1 rFIV Vaccine

rFIV vaccine is comprised of *Y. pestis* plague recombinant antigen (F1 capsular protein and the V virulence protein of *Y. pestis* Colorado 92 [CO92] fused into a single protein) adsorbed to Alhydrogel® (aluminum hydroxide).

The rF1V Plague Vaccine is a liquid formulation, containing no preservatives, in 3 mL, single dose USP Type 1 glass vials with a latex-free butyl stopper and aluminum flip-off seal containing 0.8 mL of the vaccine, and each dose of 0.5 mL contains 160 mcg rF1V, 750 mcg aluminum hydroxide (alum, Alhydrogel®) and phosphate buffer.

Please refer to the Investigator's Brochure and Pharmacy Manual for additional information.

6.1.2 CpG 1018

CpG 1018 adjuvant solution (12 mg/mL) is a clear to slightly opalescent, colorless to pale yellow liquid dosage form. CpG 1018 is formulated in 20 mM Tris, 100 mM NaCl pH 7.5 buffer. Each vial contains 6 mg of CpG 1018 formulated in 0.5 mL at a concentration of 12 mg/mL in a single-use 2 mL, clear glass vial with rubber stopper and flip-off aluminum seal.

Please refer to the rF1V Vaccine with CpG 1018 Investigator's Brochure for additional information.

6.1.3 Placebo

Placebo will be normal saline.

6.2 Instructions for Preparation and Administration

6.2.1 rFIV vaccine and CpG 1018 Preparation

Please refer to the Pharmacy Manual for additional information.

6.2.2 Study Vaccine Administration

Designated unblinded study-site personnel will be responsible for preparing and administering the study injection. These individuals will not be blinded to the treatment assignment in order to prepare and administer the study injections, which will be prepared at a location isolated from blinded personnel. These individuals will not be involved in assessing safety and laboratory data and will be instructed not to communicate treatment assignments to blinded study personnel.

The unblinded study personnel should ensure that a physical barrier is used to obstruct the view of the investigational product and that the subject turns their head away from the arm being injected to prevent the subject becoming aware of their treatment assignment.

6.2.2.1 Part 1

Group 1: 0.5 mL of rF1V vaccine and 0.25 mL of CpG 1018 will be administered intramuscularly in the same or nearby location of the deltoid muscle of the non-dominant arm on Days [REDACTED].

Group 2: 0.75 mL of the bedside mix of rF1V vaccine and CpG 1018 and 0.25 mL of placebo will be administered intramuscularly in the same or nearby location of the deltoid muscle of the non-dominant arm on Days [REDACTED]
[REDACTED]

Group 3: 0.5 mL of rF1V vaccine and 0.25 mL of placebo will be administered intramuscularly in the same or nearby location of the deltoid muscle of the non-dominant arm on Days [REDACTED]
[REDACTED]

6.2.2.2 Part 2

Scenario 1: Group 1 is selected.

Group 1: 0.5 mL of rF1V vaccine and 0.25 mL of CpG 1018 will be administered intramuscularly in the same or nearby location of the deltoid muscle of the non-dominant arm on Days [REDACTED]

Group 3: 0.5 mL of rF1V vaccine and 0.25 mL of placebo will be administered intramuscularly in the same or nearby location of the deltoid muscle of the non-dominant arm on Days [REDACTED]
[REDACTED]

Scenario 2: Group 2 is selected.

Group 2: 0.75 mL of the bedside mix of rF1V vaccine and CpG 1018 will be administered intramuscularly in the deltoid muscle of the non-dominant arm on Days [REDACTED] and 0.25 mL placebo will be administered on Day [REDACTED]

Group 3: 0.5 mL of rF1V vaccine will be administered intramuscularly in the same or nearby location of the deltoid muscle of the non-dominant arm on Days [REDACTED]

Study treatments are presented in [Table 7-1](#).

